If the patient has CB, and the cumulative kidney dose remains <23 Gy (based on the dosimetry results during Cycle 1), a third cycle may be initiated within 2 weeks after Visit 20 (Week 11) of Cycle 2, once the necessary Visit 20 (Week 11) safety follow-up assessments have been completed and reviewed. If the patient does not have CB, no further treatment will be administered and the patient will enter the long-term follow-up period.

If the patient has CB, Cycle 3 will then be initiated as follows:

- Dose 1 of CAM-H2: Visit 21 (Week 0);
- Safety Follow-Up Period: Visit 22 (Week 1), Visit 23 (Week 2), and Visit 24 (Week 3);

- Dose 2 of CAM-H2: Visit 25 (Week 4); and
- Safety Follow-Up Period: Visit 26 (Week 5), Visit 27 (Week 6), Visit 28 (Week 8), and Visit 29 (Week 11) (EOT Visit or Cycle 4 eligibility assessment).

If the patient has CB, and the cumulative kidney dose remains <23 Gy (based on the dosimetry results during Cycle 1), a fourth cycle may be initiated within 2 weeks after Visit 29 (Week 11) of Cycle 3, once the necessary Visit 29 (Week 11) safety follow-up assessments have been completed and reviewed. If the patient does not have CB, no further treatment will be administered and the patient will enter the long-term follow-up period.

If the patient has CB, Cycle 4 will then be initiated as follows:

- Dose 1 of CAM-H2: Visit 30 (Week 0);
- Safety Follow-Up Period: Visit 31 (Week 1), Visit 32 (Week 2), and Visit 33 (Week 3);
- Dose 2 of CAM-H2: Visit 34 (Week 4); and
- Safety Follow-Up Period: Visit 35 (Week 5), Visit 36 (Week 6), Visit 37 (Week 8), and Visit 38 (Week 11) (EOT Visit).

The dose escalation phase of the study will be an open-label 3 + 3 design, where at least 3 patients are treated at each dose level. Dose escalation will be done via increases of the nominal activity of CAM-H2 in cohorts of 3 to 6 patients. The dose escalation schedule is demonstrated in [Table 3](#).

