Staggered dosing will be applied for all cohorts during dose escalation. The first dose of the first patient of each cohort will be administered at least 2 weeks before the first dose of the next 2 patients (sentinel dosing). Once the MTD or RDP2 has been established, 3 additional patients will be enrolled to receive the MTD or RDP2. The patients treated at the MTD or RDP2 in the dose escalation phase will be included in the readout for efficacy. The dose escalation will be done via increases of the nominal activity of CAM-H2 in cohorts of 3 to 6 patients until approximately 15 (or a maximum of 18) patients have been dosed. The actual dose levels administered to the patient can have a tolerance window of $\pm 10\%$ of the prescribed nominal activity.

Dose escalation will be decided based on a review of all the available safety data obtained after completion of Cycle 1 (ie, after 2 IV administrations) of each dose level. If a patient is not able to complete a full cycle due to AEs related to study drug administration, he/she will not be replaced, and the dose escalation rules will be followed.

In the instance that a patient is not able to complete a full cycle due to AEs not related to study drug administration or due to a negative PD distribution scan, he/she will be replaced to ensure safety data spanning a full treatment cycle can be considered for dose escalation.

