3.1.4.1 Definition of dose-limiting toxicities

DLTs are defined as toxicities occurring **only** within Cycle 1 (ie, the approximately 12-week [84-day] period that includes 2 administrations of the study drug given 4 weeks apart [including the 4-week Safety Follow-Up Period after Dose 1]). DLTs include ≥ 1 of the following:

- Study drug-related SAE in at least 1 patient in 1 cohort;
- Severe study drug-related AE in at least 2 patients in 1 cohort;
- Any death not clearly due to the underlying disease or extraneous causes;
- Development of severe renal failure (estimated glomerular filtration rate [eGFR] <30 mL/min) or a drop of >40 mL/minute in eGFR;
- Any seizure activity that is considered to be study drug-related;
- Grade 3+ thrombocytopenia with bleeding;
- Recurrent (defined in this study as occurring after >1 dose of CAM-H2 during Cycle 1) Grade 3 or 4 thrombocytopenia;
- Grade 4+ neutropenia or thrombocytopenia >7 days;
- Recurrent (defined in this study as occurring after >1 dose of CAM-H2 during Cycle 1) Grade 3 or 4 anemia and/or neutropenia;
- Recurrent (defined in this study as occurring after >1 dose of CAM-H2 during Cycle 1) Grade 3 or 4 non-hematological toxicities as listed in the Common Terminology Criteria for Adverse Events (CTCAE) version 5.0;
- An alanine aminotransferase (ALT) or aspartate aminotransferase (AST) $>3 \times$ upper limit of normal (ULN) accompanied by a total bilirubin of $>2 \times$ ULN (Hys Law);
- Grade 3 or 4 fatigue for >1 week;
- Grade 3 or 4 electrolyte abnormalities that last >72 hours or any Grade 3 or 4 electrolyte abnormalities associated with clinical signs and symptoms of any duration;
- For patients with hepatic metastases, AST or ALT $>8 \times$ ULN or AST or ALT $>5 \times$ ULN for ≥ 14 days;
- An absorbed dose to the kidneys >23 Gy;
- An absorbed dose to the bone marrow >2 Gy; or
- Other clinically significant changes in vital signs, clinical laboratory tests, ECGs, or other safety parameters deemed as a significant safety concern by the Investigator.

All AEs of the specified grades will count as DLTs, except those that are clearly and incontrovertibly due to disease progression or extraneous causes.

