6.2.3.9 Visits 19, 28, and 37 (Week 8)

The following procedures will be performed at Visits 19, 28, and 37 (Week 8):

- Assess AEs;
- Perform physical examination;
- Measure vital signs;
- Perform clinical laboratory tests;

Note: Clinical laboratory tests should be performed prior to any imaging.

- Perform triplicate 12-lead ECGs;
- Perform urinalysis for kidney biomarkers and for microscopic evaluation of sediment;
- Assess performance status using the ECOG PS; and
- Perform imaging to evaluate disease status.

Note: Diagnostic CT scan will be performed in all patients. Brain MRI will only be performed in patients with known brain metastases.

6.2.3.10 Visits 20, 29, and 38 (Week 11): cycle eligibility or End of Treatment Visit

For Cycles 2 and 3, this visit will also serve as eligibility assessment for the next cycle in patients with CB and a cumulative kidney dose <23 Gy (based on the dosimetry results during Cycle 1). This visit will serve as the EOT Visit for patients who do not have CB and/or a cumulative kidney dose <23 Gy. This will serve as the EOT Visit for all patients in Cycle 4.

The following procedures will be performed at Visits 20, 29, and 38 (Week 11):

- Update demographics and medical history, including confirmation of lesion size;
- Record prior and concomitant medications, including information on any thyroid-blocking drugs;
- Deliver thyroid-blocking drugs for next visit (only patients eligible for and continuing to another cycle);

Note: Patients will not take the thyroid-blocking drugs at this visit but will be instructed to take them 24 hours prior to their next visit (ie, 24 hours prior to study drug administration).

- Perform urine hCG testing in all female patients of childbearing potential (ie, ovulating, premenopausal, and not surgically sterile);
- Collect blood to evaluate serum for ADAs and to measure exploratory biomarkers (from patients who have consented to the procedure);

Note: Clinical laboratory tests should be performed prior to any imaging.

- Assess AEs;
- Measure weight;
- Perform physical examination;
- Measure vital signs;
- Perform clinical laboratory tests;

Note: Clinical laboratory tests should be performed prior to any imaging.

- Perform triplicate 12-lead ECGs;
- Perform echocardiogram;

Note: LVEF may alternatively be measured using a multigated acquisition scan.

- Perform urinalysis for kidney biomarkers and for microscopic evaluation of sediment; and

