- Perform imaging to evaluate disease status (EOT Visit only).

Note: Diagnostic CT scan will be performed in all patients. Brain MRI will only be performed in patients with known brain metastases.

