Table 8. Schedule of Procedures: Dose Escalation Phase, Cycles 2, 3, and 4 (Continued)

Footnotes at end of table.

Table 8. Schedule of Procedures: Dose Escalation Phase, Cycles 2, 3, and 4 (Continued)

Study Period	Cycle Eligibility ^a	Treatment Period Cycles 2, 3, and 4												LT FU ^d			
		Dose 1			Safety FU			Dose 2			Safety FU						
Week	W-2 to W-1	W0			W1	W2	W3	W4			W5	W6	W8	W11 ^c (EOT/Eligibility Assess for Next Cycle)			
Days Relative to Dose Administration	D-14 to D0	D1 to D3			D8	D15	D22	D1 ^b to D3			D8	D15	D29	D50			
Visit Number (Cycle 2)	V11	V12			V13	V14	V15	V16			V17	V18	V19	V20			
Visit Number (Cycle 3)	V20	V21			V22	V23	V24	V25			V26	V27	V28	V29			
Visit Number (Cycle 4)	V29	V30			V31	V32	V33	V34			V35	V36	V37	V38			
Visit Window (Days)	-	±3			±1	±3	±3	±3			±3	±3	+7	±7			
		Pre	0 m	30 m	3 h	5 h	24 h	48 h			Pre	0 m	30 m	3 h	5 h	24 h	48 h
CAM-H2 administration procedures																	
Radioactive unit admission ^q		X-----X							X-----X								
Premedication therapy ^r		X							X								
Saline infusion ^s		X-----X							X-----X								
Amino acid infusion ^t		X-----X							X-----X								
Study drug administration ^u			X---X						X-----X								
Imaging to evaluate organ/target lesion uptake ^v																	
Planar WB scan						X ^w					X						
Imaging to evaluate disease status ^x																	
Diagnostic CT scan												X	X ^z	X			
Brain MRI ^y												X	X ^z	X			

Footnotes on the next page.

- a. The eligibility assessment for Cycle 2 is the same visit as the EOT/Cycle eligibility assessment in Cycle 1 of the dose escalation phase. (See [Table 7](#)).
- b. Dose 2 will begin 1 week (7 days) after the end of Dose 1 Safety FU Period. However, if a patient misses a dose of study drug due to study drug production problems or due to other circumstances (in certain cases), the interval between doses may be extended up to 6 weeks (Cycle 2) or up to 12 weeks (Cycles 3 and 4). Safety FU visits after Dose 2 will be scheduled based on the actual Dose 2 visit date.
- c. For Cycles 2 and 3, if the patient has CB and the cumulative kidney dose remains <23 Gy (based on the dosimetry results during Cycle 1), the patient will not undergo an EOT Visit but proceed to the next cycle's (ie, Cycle 3 or Cycle 4) Cycle Eligibility visit. If the patient does not have CB or if this is Cycle 4, the patient will undergo an EOT Visit and no further treatment will be administered. The patient will enter the LT FU period.

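### The 23 Gy kidney limit on repeat cycles never says whether the coming cycle's projected dose counts, and Section 6.2.3.10 can be read as dose to date

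*Combined protocol and SAP*

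**What the plan says.** Protocol Section 1.3.2 sets 23 Gy as the absorbed-dose limit for the kidneys and says radiotoxicity could occur above it. Escalation patients with CB may have up to four cycles and expansion patients up to two, subject to that limit.

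The condition is worded in two ways:

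- **Most places use *remains*.** Section 3.1.1.2 says of entry to Cycle 4 that if "the cumulative kidney dose remains <23 Gy (based on the dosimetry results during Cycle 1), a fourth cycle may be initiated". Table 8 footnote c covers the same visits: "For Cycles 2 and 3, if the patient has CB and the cumulative kidney dose remains <23 Gy". The Synopsis, Sections 3.1, 3.1.2.2 and 5.1, and footnote d of Tables 7 and 9 use the same verb.
- **Section 6.2.3.10 drops it.** For Visits 20 and 29 it describes an "eligibility assessment for the next cycle in patients with CB and a cumulative kidney dose <23 Gy".

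The EOT routing also differs. Section 6.2.3.10 says: "This visit will serve as the EOT Visit for patients who do not have CB and/or a cumulative kidney dose <23 Gy". Table 8 footnote c says: "If the patient does not have CB or if this is Cycle 4, the patient will undergo an EOT Visit", with no mention of the kidney check. Disease imaging at Week 11 depends on this label, because Section 6.2.3.10 lists it as "Perform imaging to evaluate disease status (EOT Visit only)".

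The Visit 11 sections (6.2.2.9 and 6.3.2.9) do not name the 23 Gy check and give an explicit EOT route only to patients without CB.

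**The concern.** A cumulative limit checked before treatment can mean two things: the dose already received is below 23 Gy, or the dose received plus the dose about to be given is below 23 Gy. The protocol neither defines the cumulative kidney dose nor gives a projection formula.

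The reference to Cycle 1 dosimetry does not settle the matter. Table 1 schedules no SPECT/CT in Cycles 2 to 4, so even completed later cycles have to be extrapolated from Cycle 1.

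The stake is a renal safety limit. If site staff take Section 6.2.3.10 as dose to date, a patient below 23 Gy at the visit could start a cycle that ends well above it. The routing gap is smaller: a patient with CB stopped by the kidney check has an EOT Visit under one text and none under the other.

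**Working it through.** **Inputs.** Kidney dose of 34.9 ± 2 mGy/mCi, predicted, and the 23 Gy limit (Section 1.3.2). Activity of 100, 200, 300 and 400 mCi per cycle at Levels 1 to 4 (Table 3). Assumption: every cycle delivers the Cycle 1 dose, with no dose reductions.

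**The plan's own figures.** 400 × 34.9 / 1000 = 13.96 Gy (stated: 14 Gy). 23 / 0.0349 = 659.0 mCi (stated: 659 mCi). Both reproduce.

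**Rules compared.** Let d be the kidney dose per cycle and k the number of cycles completed. Dose to date admits the next cycle if k × d < 23. Projection admits it if (k + 1) × d < 23.

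| Level | d (Gy) | Cycles allowed, dose to date | Final Gy | Cycles allowed, projection | Final Gy |
|---|---|---|---|---|---|
| 1 | 3.49 | 4 | 13.96 | 4 | 13.96 |
| 2 | 6.98 | 4 | 27.92 | 3 | 20.94 |
| 3 | 10.47 | 3 | 31.41 | 2 | 20.94 |
| 4 | 13.96 | 2 | 27.92 | 1 | 13.96 |

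The excess over the limit is 27.92 − 23 = 4.92 Gy at Levels 2 and 4 and 31.41 − 23 = 8.41 Gy at Level 3. At Levels 2 and 3 the first administration of the disputed cycle already crosses it: 20.94 + 3.49 = 24.43 Gy and 20.94 + 5.235 = 26.18 Gy. At Level 4 the second one does: 13.96 + 6.98 = 20.94, then 27.92 Gy.

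**Sensitivity to the coefficient.** At 32.9 and 36.9 mGy/mCi and nominal activity, the same cycles are disputed. Final doses under dose to date are 26.32 to 29.52 Gy (Level 2), 29.61 to 33.21 Gy (Level 3) and 26.32 to 29.52 Gy (Level 4).

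**Sensitivity to activity.** Section 3.1.1.2 adds: "The actual dose levels administered to the patient can have a tolerance window of" ±10%. At 34.9 mGy/mCi:

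- At −10% the same cycles are disputed, ending at 25.13 Gy (Level 2), 28.27 Gy (Level 3) and 25.13 Gy (Level 4).
- At +10% the dispute moves one cycle earlier for Level 2 (Cycle 3, 15.36 to 23.03 Gy) and Level 3 (Cycle 2, 11.52 to 23.03 Gy). The switch comes at (23/3) / 6.98 = (23/2) / 10.47 = 1.098, that is, +9.8%.
- Level 4 stays at Cycle 2 entry (15.36 to 30.71 Gy at +10%).

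**Without any coefficient.** The readings differ whenever k × d < 23 ≤ (k + 1) × d:

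- Cycle 4 entry: d from 5.75 to below 7.67 Gy, ending at 23 to below 30.67 Gy.
- Cycle 3 entry: d from 7.67 to below 11.5 Gy, ending at 23 to below 34.5 Gy.
- Cycle 2 entry: d from 11.5 to below 23 Gy.

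Section 6.2.3.10 covers the first two. Cycle 2 entry rests on the *remains* wording, so the ambiguity there is weaker.

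**The case against.** The best defence is that Section 6.2.3.10 describes what the visit is for and does not authorise dosing. Permission to start a cycle sits in Section 3.1.1.2, with Section 5.1 in support. There the dose must *remain* below 23 Gy as a condition of receiving up to four cycles, which reads naturally as a cap on the total. Section 6.2.3.10 uses the same threshold and the same dosimetry basis, so it may be shorthand with one word dropped. Dosimetry detail is also deferred to the Imaging Review Charter, which is not available here and might define the calculation.

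Much of this stands, and it rules out three stronger conclusions that a reader might draw:

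- **That the protocol authorises exceeding 23 Gy.** It does not. A patient who meets Section 6.2.3.10 must still meet Section 3.1.1.2, whose wording favours projection.
- **That no absorbed-dose limit applies after Cycle 1.** The dose-limiting toxicity criterion "An absorbed dose to the kidneys >23 Gy" does count only within Cycle 1, but the cumulative 23 Gy condition is itself a limit on later cycles. Section 3.1.5.2 also requires withholding at eGFR below 40 mL/minute or a 40% fall, resumption at 50%, and permanent discontinuation for long delay or recurrence. Those renal rules act only after exposure.
- **That Section 6.2.3.10 is unworkable under either intent.** If projection is meant, a patient with CB at 20.9 Gy attends the assessment and is refused the next cycle under Section 3.1.1.2. Only the EOT label and its scan are left unclear, and disease imaging every 8 weeks continues.

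What the defence does not supply is a stated rule. Projection remains an inference from one verb, and the section written for the visit omits that verb.

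**Conclusion.** The point holds as a missing definition, with a mild wording inconsistency that makes it matter. Nothing in the protocol says whether the coming cycle counts toward 23 Gy, and the two readings give different treatment decisions at Levels 2, 3 and 4. Under dose to date, the final kidney dose is 27.9 Gy (Level 2, Cycle 4), 31.4 Gy (Level 3, Cycle 3) and, if applied at Cycle 2 entry, 27.9 Gy (Level 4). Level 1 is unaffected.

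These figures assume nominal activity, equal additive cycles without reductions, and the predicted mean coefficient. Measured Cycle 1 dosimetry may move or remove the disputed cycle for a given dose level.

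Few patients are exposed through Section 6.2.3.10. Escalation has at most 18 patients, and an affected patient needs CB through three cycles at Level 2 or two at Level 3. Cycle 2 entry would matter more widely if Level 4 were taken into expansion.

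The mismatch in EOT routing between Table 8 footnote c and Section 6.2.3.10 stands whichever reading is intended. This is a low-cost clarification of a safety rule.

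**What to change.** State one rule: a further cycle may start only if the cumulative kidney dose to date plus the projected dose of the next cycle is below 23 Gy, and all other patients have the EOT Visit with its existing EOT imaging. The projection uses Cycle 1 dosimetry in escalation, and escalation Cycle 1 dosimetry for expansion patients.

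Use the same phrase in the Synopsis, Sections 3.1, 3.1.1.2, 3.1.2.2, 5.1, 6.2.2.9, 6.2.3.10 and 6.3.2.9, and the Appendix A footnotes. The Week 11 scan notes under Tables 1 and 2, and their Synopsis copies, name only patients without CB and should be matched.

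If the sponsor's clinicians do intend dose to date, the protocol should say so and state the highest total kidney dose accepted.

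The cost is a text amendment across several sections. The 23 Gy limit, the cycle ceilings and the dosimetry schedule do not change. There are two downsides: some patients with CB receive one cycle fewer than under dose to date, and patients with CB stopped by the kidney check have the EOT scan at Week 11.

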6.3 Dose Expansion Phase

6.3.1 Screening for the Dose Expansion Phase

6.3.1.1 Visit 1 (Week -4 to Week -1)

The following procedures will be performed at the first screening visit (Week -4 to Week -1) prior to the initiation of the dose expansion phase:

- Obtain informed consent;
- Assess inclusion and exclusion criteria;
- Record demographics and medical history, including confirmation of lesion size;
- Record prior and concomitant medications, including information on any thyroid-blocking drugs;
- Perform serum hCG testing in all female patients of childbearing potential (ie, ovulating, premenopausal, and not surgically sterile);
- Assess AEs;
- Measure height and weight;
- Perform physical examination;
- Measure vital signs;
- Perform clinical laboratory tests;
- Perform triplicate 12-lead ECGs;
- Perform echocardiogram;

Note: LVEF may alternatively be measured using a multigated acquisition scan.

- Perform urinalysis for kidney biomarkers and for microscopic evaluation of sediment;
- Assess performance status using the ECOG PS; and
- Perform imaging to evaluate disease status.

Note: Diagnostic CT scan will be performed in all patients. Brain MRI will only be performed in patients with known brain metastases.

6.3.1.2 Visit 2 (Week -1)

The following procedures will be performed preferably within the 14 days prior to study drug administration:

- Deliver thyroid-blocking drugs;

Note: Patients will not take the thyroid-blocking drugs at this visit but will be instructed to take them 24 hours prior to their next visit (ie, 24 hours prior to study drug administration).

- Perform serum hCG testing in all female patients of childbearing potential (ie, ovulating, premenopausal, and not surgically sterile);

- Collect blood to evaluate serum for ADAs and to measure exploratory biomarkers (from patients who have consented to the procedure);
- Assess AEs;
- Perform clinical laboratory tests; and
- Perform urinalysis for kidney biomarkers and for microscopic evaluation of sediment.

6.3.2 Cycle 1 of the Dose Expansion Phase

6.3.2.1 Visit 3 (Week 0)

Dose 1 of Cycle 1 will be administered at Visit 3. The following procedures will be performed at Visit 3 (Week 0):

- Admit to radioactive unit for hospitalization prior to study drug administration;

Note: Patients will be admitted during each IV administration for a total of 48 hours. This hospitalization can be shortened if ^{131}I decay and the patient's clearance allow discharge according to the applicable local regulations on radioactive compound exposure.

Note: Before the patient is released, a leaflet containing information on radioprotection rules and general precautions after radiation treatment will be distributed (see [Appendix F](#)).

- Confirm the ingestion of thyroid-blocking drugs at least 24 hours prior to study drug administration;
- Deliver and confirm the ingestion of thyroid-blocking drugs 1 hour prior to study drug administration;
- Deliver and confirm the ingestion of thyroid-blocking drugs 24 and 48 hours after study drug administration;

Note: If the patient is discharged prior to 48 hours, deliver the thyroid-blocking drugs for 48 hours at 24 hours. Patients will still take the thyroid-blocking drugs 48 hours after study drug administration.

- Perform urine hCG testing in all female patients of childbearing potential (ie, ovulating, premenopausal, and not surgically sterile) prior to study drug administration;
- Assess AEs;
- Perform physical examination prior to study drug administration and at 24 hours after study drug administration;
- Measure vital signs prior to study drug administration and 30 minutes, 5 hours, 24 hours, and 48 hours after study drug administration;
- Administer anti-emetic, anti-histamine, and anti-pyretic premedication therapy approximately 30 minutes prior to the start of the amino acid infusion, according to the site's standard operating procedures;
- Administer saline 0.9% infusion, starting 30 minutes prior to study drug administration and continuing for up to 3 hours after, at a rate of 200 to 300 mL/hour;

- Administer an amino acid solution beginning 30 minutes prior to study drug administration and ending 3 hours after study drug administration at a rate of 250 to 500 mL/hour;
- Administer study drug via slow IV infusion, ie, administer using a shielded infusion device over approximately 3 to 30 minutes, depending on the volume to be injected; and
- Perform a planar WB scan and a SPECT/CT scan 24 (± 4) hours after study drug administration. The planar WB scan done at this visit will also serve as the PD distribution scan.

